**Table 7.4.3.1-1: Adverse Event Criteria for Delay, Resume, and Discontinue of Nivolumab and/or BMS-986288**

Drug-Related Adverse Event (AE) per CTCAE v5	Severity	Action Taken	Clarifications, Exceptions, and Resume Criteria
			Grade 2 pneumonitis that does not respond to dose delay and systemic steroids within 14 days is a DLT.
	Grade 3 or 4	Permanently discontinue	
Hepatic			
Aspartate aminotransferase (AST), alanine aminotransferase (ALT), or total bilirubin (T.bili) increased	AST or ALT > 3x and $\leq 5$ x upper limit of normal (ULN) or T.Bili > 1.5x and $\leq 3$ x ULN, regardless of baseline value	Delay dose	Dosing may resume when laboratory values return to baseline.
	AST or ALT > 5 x ULN or T. bili > 3 x ULN, regardless of baseline value	Delay dose or Permanently discontinue	In most cases of AST or ALT > 5 x ULN, study treatment will be permanently discontinued. If the investigator determines a possible favorable benefit/risk ratio that warrants continuation of study treatment, a discussion between the investigator and the Medical Monitor/ designee must occur and approval from Medical Monitor prior to resuming therapy.
	Concurrent AST or ALT > 3 x ULN and T.bili > 2 x ULN, regardless of baseline value	Permanently discontinue	
Endocrinopathy			
Adrenal Insufficiency	Grade 2 adrenal insufficiency	Delay dose	Dosing may resume after adequately controlled with hormone replacement.
	Grade 3 or 4 adrenal insufficiency or adrenal crisis	Delay dose or permanently discontinue	Mandatory discussion with and approval from the Medical Monitor needed prior to resuming therapy. If adrenal insufficiency resolves or is adequately controlled with physiologic hormone replacement, participant may not require discontinuation of study drug.
Hyperglycemia	Hyperglycemia requiring initiation or change in daily management (Grade 2 or 3)	Delay dose	Dosing may resume if hyperglycemia resolves to Grade $\leq 1$ or baseline value, or is adequately controlled with glucose-controlling agents.
	Grade 4	Delay dose or permanently discontinue	Mandatory discussion with and approval from the Medical Monitor needed prior to resuming therapy. If hyperglycemia resolves, or is adequately controlled with glucose-

**Table 7.4.3.1-1: Adverse Event Criteria for Delay, Resume, and Discontinue of Nivolumab and/or BMS-986288**

Drug-Related Adverse Event (AE) per CTCAE v5	Severity	Action Taken	Clarifications, Exceptions, and Resume Criteria
			controlling agents, participant may not require discontinuation of study drug.
Hypophysitis/Hypopituitarism	Symptomatic Grade 1-3 that is also associated with corresponding abnormal lab and/or pituitary scan	Delay dose	Dosing may resume if endocrinopathy resolves to be asymptomatic, or is adequately controlled with only physiologic hormone replacement.
	Grade 4	Delay dose or permanently discontinue	Mandatory discussion with and approval from the Medical Monitor needed prior to resuming therapy. If endocrinopathy resolves or is adequately controlled with physiologic hormone replacement, participant may not require discontinuation of study drug.
Hyperthyroidism or Hypothyroidism	Grade 2 or 3	Delay dose	Dosing may resume if endocrinopathy resolves to be asymptomatic, or is adequately controlled with only physiologic hormone replacement or other medical management.
	Grade 4	Delay dose or permanently discontinue	Mandatory discussion with and approval from the Medical Monitor needed prior to resuming therapy. If endocrinopathy resolves or is adequately controlled with physiologic hormone replacement or other medical management, participant may not require discontinuation of study drug.
Skin			
Rash	Grade 2 rash covering > 30% body surface area or Grade 3 rash	Delay dose	Dosing may resume when rash reduces to ≤10% body surface area.

**Table 7.4.3.1-1: Adverse Event Criteria for Delay, Resume, and Discontinue of Nivolumab and/or BMS-986288**

Drug-Related Adverse Event (AE) per CTCAE v5	Severity	Action Taken	Clarifications, Exceptions, and Resume Criteria
	Suspected Stevens-Johnson syndrome (SJS), toxic epidermal necrolysis (TEN), or drug reaction with eosinophilia and systemic symptoms (DRESS)	Discontinue or delay dose	Dosing may resume if SJS, TEN, or DRESS is ruled out and rash reduces to $\leq 10\%$ body surface area.
	Grade 4 rash or confirmed SJS, TEN, or DRESS	Permanently discontinue	
Neurological			
Guillain-Barre Syndrome (GBS)	Any Grade	Permanently discontinue	
Myasthenia Gravis (MG)	Any Grade	Permanently discontinue	
Encephalitis	Any Grade encephalitis	Delay dose	After workup for differential diagnosis, (ie, infection, tumor-related), if encephalitis is not drug related, then dosing may resume when AE resolves.
	Any Grade drug-related encephalitis	Permanently discontinue	
Myelitis	Any Grade myelitis	Delay dose	After workup for differential diagnosis, (ie, infection, tumor-related), if myelitis is not drug related, then dosing may resume when AE resolves.
	Any Grade drug-related myelitis	Permanently discontinue	
Neurological (other than GBS, MG, encephalitis, or myelitis)	Grade 2	Delay dose	Dosing may resume when AE resolves to baseline.
	Grade 3 or 4	Permanently discontinue	
Myocarditis			
Myocarditis	Symptoms induced from mild to moderate activity or exertion	Delay dose	Dosing may resume after myocarditis has resolved.
	Severe or life threatening, with symptoms at rest or with minimal activity or exertion, and/or where intervention indicated.	Permanently discontinue	

**Table 7.4.3.1-1: Adverse Event Criteria for Delay, Resume, and Discontinue of Nivolumab and/or BMS-986288**

Drug-Related Adverse Event (AE) per CTCAE v5	Severity	Action Taken	Clarifications, Exceptions, and Resume Criteria
Other Clinical AE			
Pancreatitis: Amylase or Lipase increased	Grade 3 with symptoms	Delay dose	Note: Grade 3 increased amylase or lipase without signs or symptoms or radiographic evidence of pancreatitis does not require dose delay. Dosing may resume when patient becomes asymptomatic.
	Grade 4	Permanently discontinue	Grade 4 increased amylase or lipase without signs or symptoms or radiographic evidence of pancreatitis does not require permanent discontinue.
Uveitis, episcleritis, iritis, eye pain, or blurred vision	Grade 2	Delay dose	Dosing may resume with response to topical therapy (eye drops) and after resolution to Grade $\leq$ 1 or baseline. If patient requires oral steroids, then permanently discontinue study drug.
	Grade 3 or 4	Permanently discontinue	
Other Drug-related AE (not listed above)	Grade 2 non-skin AE, except fatigue	Delay dose	Dosing may resume when AE resolves to Grade $\leq$ 1 or baseline value.
	Grade 3 AE - First occurrence lasting $\leq$ 7 days	Delay dose	Dosing may resume when AE resolves to Grade $\leq$ 1 or baseline value.
	Grade 3 AE- First occurrence lasting $>$ 7 days	Permanently discontinue	
	Recurrence of Grade 3 AE of any duration	Permanently discontinue	Exception to permanent discontinue: Grade 3 fatigue $<$ 7 days in any cycle does not require permanent discontinue. Grade 3 tumor flare (defined as pain, irritation, or rash that localizes to sites of known or suspected tumor). Grade 3 fever not associated with hemodynamic compromise (eg, hypotension, clinical, or laboratory evidence of impaired end-organ perfusion). Grade 3 nausea, vomiting, or abdominal pain that returns to Grade 1 or baseline within 48 hours, either spontaneously or with medical intervention.
	Grade 4 or Life-threatening adverse reaction	Permanently discontinue	

**Table 7.4.3.1-1: Adverse Event Criteria for Delay, Resume, and Discontinue of Nivolumab and/or BMS-986288**

Drug-Related Adverse Event (AE) per CTCAE v5	Severity	Action Taken	Clarifications, Exceptions, and Resume Criteria
Other Lab abnormalities			
Other Drug-Related lab abnormality (not listed above)	Grade 3	Delay dose	Exception: No delay required for Grade 3 lymphopenia.
	Grade 4	Permanently discontinue	Exceptions: The following events do not require discontinuation of study drug: 
 
• Grade 4 lymphopenia or leukopenia. Grade 4 lymphopenia or leukopenia that lasts > 7 day is a DLT.
 
• Grade 3 or 4 isolated electrolyte imbalances/abnormalities that are not associated with clinical sequelae and are responding to supplementation/appropriate management within 72 hours of their onset.
 

Infusion Reactions (manifested by fever, chills, rigors, headache, rash, pruritus, arthralgia, hypotension, hypertension, bronchospasm, or other allergic-like reactions.)			
Hypersensitivity reaction or infusion reaction	Grade 3 or 4	Permanently discontinue	Refer to Section 7.4.5 on Treatment of Related Infusion Reactions

#### **7.4.4      *Exceptions to Permanent Discontinuation Criteria***

Any drug-related AE occurring at any time that meets DLT criteria as outlined in [Section 7.4.1](#) will require permanent discontinuation, with the exceptions detailed in [Table 7.4.3.1-1](#) and the following:

- Any event that leads to delay in dosing, lasting > 8 weeks from the previous dose, requires discontinuation, with the exception of the following:
  - Dosing delays for prolonged steroid tapers to manage drug-related AEs are allowed. Prior to re-initiating treatment in a participant with a dosing delay lasting > 8 weeks from the previous dose, the BMS Medical Monitor (or designee) must be consulted. Tumor assessments should continue as per protocol even if dosing is delayed. Periodic study visits to assess safety and laboratory studies should also continue [REDACTED], or more frequently if clinically indicated, during such dosing delays.
  - Dosing delays lasting > 8 weeks from the previous dose that occur for non-drug-related reasons may not require discontinuation, if approved by the BMS Medical Monitor (or designee). Prior to re-initiating treatment in a participant with a dosing delay lasting > 8 weeks, the BMS Medical Monitor (or designee) must be consulted.

Even if the criteria to resume treatment are met, the consideration to re-initiate study therapy under the following exception will be made on a case-by-case basis after considering the overall benefit/risk profile and in consultation between the Investigator and the Sponsor. Any AE with clinical risk will be assessed on a case-by-case basis with the Investigator and the BMS Medical Monitor (or designee) to determine the risks and benefits of continuing on therapy following resolution vs discontinuing therapy permanently.

#### **7.4.5      *Management of Drug-related Infusion Reactions***

Because BMS-986288 and nivolumab contain only human Ig protein sequences, they are unlikely to be immunogenic and induce infusion or hypersensitivity reactions. However, based on the non-clinical toxicology evaluation of BMS-986288, infusion reactions due to [REDACTED] activation and cytokine release may occur in both monotherapy and combination with nivolumab. If such a reaction were to occur, it might manifest with fever, chills, rigors, headache, rash, pruritus, arthralgia, hypotension, hypertension, bronchospasm, or other allergic-like reactions. Report all Grade 3 or 4 infusion reactions within 24 hours as an SAE if it meets the criteria.

Treatment recommendations for infusion reactions are provided below and may be modified based on local treatment standards and guidelines, as appropriate.

**For Grade 1 symptoms** (mild reaction, infusion interruption not indicated, intervention not indicated), recommendations are as follows:

- Remain at bedside and monitor participant until recovery from symptoms. The following prophylactic premedications are recommended for future infusions: diphenhydramine 50 mg (or equivalent) and/or acetaminophen/paracetamol 325 to 1,000 mg at least 30 minutes before study treatment administrations.

**For Grade 2 symptoms** (moderate reaction requiring therapy or infusion interruption but responding promptly to symptomatic treatment such as antihistamines, non-steroidal anti-inflammatory drugs, narcotics, corticosteroids, bronchodilators, IV fluids, or prophylactic medications indicated for  $\leq$  24 hours), recommendations are as follows:

- Stop the study treatment infusion, begin an IV infusion of normal saline, and treat the participant with diphenhydramine 50 mg IV (or equivalent) and/or acetaminophen/paracetamol 325 to 1,000 mg; remain at bedside and monitor participant until resolution of symptoms. Corticosteroid and/or bronchodilator therapy may also be administered as appropriate. If the infusion is interrupted, then restart the infusion at 50% of the original infusion rate when symptoms resolve; if no further complications ensue after 30 minutes, then the rate may be increased to 100% of the original infusion rate. Monitor participant closely. If symptoms recur, then no further BMS-986288 or nivolumab will be administered at that visit.
- For future infusions, the following prophylactic premedications are recommended: diphenhydramine 50 mg (or equivalent) and/or acetaminophen/paracetamol 325 to 1,000 mg should be administered at least 30 minutes before study treatment infusions. If necessary, corticosteroids (up to 25 mg of hydrocortisone or equivalent) may be used.

**Grade 3 or 4** infusion reactions require permanent discontinuation of both study treatments.

**For Grade 3 or 4 symptoms** (severe reaction, Grade 3: prolonged [ie, not rapidly responsive to symptomatic medication and/or brief interruption of infusion]; recurrence of symptoms after initial improvement; hospitalization indicated for other clinical sequelae [eg, renal impairment, pulmonary infiltrates]; Grade 4: life-threatening; pressor or ventilatory support indicated), recommendations are as follows:

- Immediately discontinue [REDACTED] study treatment. Begin an IV infusion of normal saline and treat the participant as follows: recommend bronchodilators, epinephrine 0.2 to 1 mg of a 1:1,000 solution for SC administration or 0.1 to 0.25 mg of a 1:10,000 solution injected slowly for IV administration, and/or diphenhydramine 50 mg IV with methylprednisolone 100 mg IV (or equivalent), as needed. Participant should be monitored until the Investigator is comfortable that the symptoms will not recur. Investigators should follow their institutional guidelines for the treatment of anaphylaxis. Remain at bedside and monitor participant until recovery of the symptoms.

In case of late-occurring hypersensitivity symptoms (eg, appearance of a localized or generalized pruritus within 1 week after treatment), symptomatic treatment may be given (eg, oral antihistamine or corticosteroids).

#### **7.4.6 Dose Modification for Regorafenib**

If dose modifications are required, reduce the dose in 40 mg (one tablet) increments; the lowest recommended daily dose of regorafenib is 80 mg daily. The following dose modification is provided as a recommendation. Local product labels and/or institutional guidelines should be followed if they are more conservative than the recommendations below.

Interrupt regorafenib for the following:

- Grade 2 hand-foot skin reaction (HFSR) (palmar-plantar erythrodysesthesia syndrome) that is recurrent or does not improve within 7 days despite dose reduction; interrupt therapy for a minimum of 7 days for Grade 3 HFSR. If restarting treatment, decrease dose by 40 mg.
- Symptomatic Grade 2 hypertension.
- Any Grade 3 or 4 adverse reaction.
- Worsening infection of any grade.

Reduce the dose of regorafenib to [REDACTED] mg:

- For the first occurrence of Grade 2 HFSR of any duration.
- After recovery of any Grade 3 or 4 adverse reaction except infection.
- For Grade 3 AST/ALT elevation, only resume if the potential benefit outweighs the risk of hepatotoxicity.

Reduce the dose of regorafenib to 80 mg:

- For re-occurrence of Grade 2 HFSR at the 120-mg dose.
- After recovery of any Grade 3 or 4 adverse reaction at the 120-mg dose (except hepatotoxicity or infection).

Discontinue regorafenib permanently for the following:

- Failure to tolerate 80-mg dose.
- Any occurrence of AST or ALT more than  $20 \times$  ULN.
- Any occurrence of AST or ALT more than  $3 \times$  ULN with concurrent bilirubin more than  $2 \times$  ULN.
- Re-occurrence of AST or ALT more than  $5 \times$  ULN despite dose reduction to 120 mg.
- Gastrointestinal perforation or fistula.
- Severe or life-threatening hemorrhage.
- Reversible posterior leukoencephalopathy syndrome.
- Wound dehiscence.
- Any event that leads to delay in dosing for  $> 8$  weeks from the previous dose requires discontinuation with the following exception: dosing delays  $> 8$  weeks that occur for non-drug-related reasons may be allowed if approved by the BMS Medical Monitor. Prior to re-initiating treatment in a participant with a dosing delay lasting  $> 8$  weeks, the BMS Medical Monitor must be consulted. Tumor assessments should continue as per protocol even if dosing is delayed.
- Any AE, laboratory abnormality, or intercurrent illness which, in the judgment of the investigator, presents a substantial clinical risk to the participant with continued treatment.

- For any Grade 4 adverse reaction, only resume if the potential benefit outweighs the risks.

## **7.5 Preparation/Handling/Storage/Accountability**

The IP should be stored in a secure area according to local regulations. It is the responsibility of the Investigator to ensure that IP is only dispensed to study participants. The IP must be dispensed only from official study sites by authorized personnel according to local regulations.

The product storage manager should ensure that the study treatment is stored in accordance with the environmental conditions (temperature, light, and humidity) as determined by BMS. If concerns regarding the quality or appearance of the study treatment arise, the study treatment should not be dispensed and contact BMS immediately.

Study treatment not supplied by BMS will be stored in accordance with the package insert.

IP documentation (whether supplied by BMS or not) must be maintained that includes all processes required to ensure drug is accurately administered. This includes documentation of drug storage, administration and, as applicable, storage temperatures, reconstitution, and use of required processes (eg, required diluents, administration sets).

Storage facilities for controlled substances must be securely locked and substantially constructed, with restricted access to prevent theft or diversion, as applicable by local regulations.

- Further guidance and information for final disposition of unused study treatment are provided in [Appendix 2](#) and the Pharmacy Manual.

Please refer to the current version of the IBs █ and/or Pharmacy Manual for complete preparation, storage, and handling information.

When study treatments nivolumab and BMS-986288 are to be administered on the same day, nivolumab is to be administered first. Nivolumab infusion must be promptly followed by a flush of diluent to clear the line of nivolumab before starting the BMS-986288 infusion. The second infusion will always be the BMS-986288 study treatment and will start after the infusion line has been flushed, filters changed, and the participant has been observed to ensure no infusion reaction has occurred.

### **7.5.1 Retained Samples for Bioavailability/Bioequivalence**

Not applicable.

## **7.6 Treatment Compliance**

Not applicable.

## **7.7 Concomitant Therapy**

### **7.7.1 Prohibited and/or Restricted Treatments**

The following medications are prohibited during the study (unless utilized to treat a drug-related AE):

- Immunosuppressive agents.

- Immunosuppressive doses of systemic corticosteroids (except as stated in [Section 6.2](#)).
- Any concurrent approved or investigational anti-neoplastic therapy (eg, chemotherapy, immunotherapy, extensive, non-palliative radiation therapy). Palliative hormonal therapy will be permitted when indicated.
- Any botanical preparation (eg, herbal supplements or traditional Chinese medicines) intended to treat the disease under study. Use of marijuana and its derivatives for treatment of symptoms related to cancer or cancer treatment are permitted if obtained by medical prescription or if its use (even without a medical prescription) has been legalized locally.
- Any live/attenuated vaccine (eg, varicella, zoster, yellow fever, rotavirus, oral polio and measles, mumps, rubella [MMR]) during treatment and until 100 days post last dose.
- Administration of investigational SARS-CoV-2 vaccines is not allowed during the study.
- Treatment of active SARS-CoV-2 infections or high-risk exposures, including use of investigational therapies, is allowed and should be discussed with the medical monitor.
- Participants may receive authorized or approved SARS-CoV-2 vaccines while continuing on study treatment at the discretion of the Investigator.

#### **7.7.1.1 *Imaging Restriction and Precautions***

It is the local imaging facility's responsibility to determine, based on participant attributes (eg, allergy history, diabetic history, renal status), the appropriate imaging modality and contrast regimen per imaging study. Imaging contraindications and contrast risks are to be considered in this assessment. Participants with renal insufficiency are to be assessed as to whether or not they should receive contrast, and if so, which contrast agent and dose is appropriate. Specific to MRI, participants with severe renal insufficiency (ie, estimated glomerular filtration rate [eGFR] < 30 mL/min/1.73 m^2) are at increased risk of nephrogenic systemic fibrosis; therefore, MRI contrast is contraindicated. In addition, participants may be excluded from MRI if they have tattoos, metallic implants, pacemakers, etc. This will be outlined in the Image Acquisition Manual.

Gentle hydration before and after IV contrast should follow local standard of care. The ultimate decision to perform MRI in an individual participant in this study rests with the site radiologist, the Investigator, and standards set by the local Ethics Committee.

#### **7.7.2 *Permitted Therapy***

Participants are permitted the use of the following treatments:

- Topical, ocular, intra-articular, intra-nasal, and inhalational corticosteroids (with minimal systemic absorption).
- Adrenal replacement steroid doses  $\geq$  10 mg daily prednisone equivalent.
- A brief (less than 3 weeks) course of corticosteroids for prophylaxis (eg, contrast dye allergy) or for treatment of non-autoimmune conditions (eg, delayed-type hypersensitivity reaction caused by a contact allergen).
- Supportive care: For participants receiving regorafenib, follow local product label, institutional guidelines, or relevant regional guidelines (eg, American Society of Clinical Oncology or European Society for Medical Oncology) to manage expected toxicities. Supportive care includes, but is not limited to, hematologic support and management of diarrhea,

nausea/vomiting, skin toxicities, as well as prophylactic or therapeutic administration of appropriate therapies.

### **7.7.3 Palliative Local Therapy**

Palliative and supportive care for disease-related symptoms may be offered to all participants on the study. Limited radiation treatment or surgery to control isolated lesions may be permitted for participants following consultation with the BMS Medical Monitor (or designee).

Participants should not receive study treatment during radiation because the potential for overlapping toxicities with radiotherapy and study treatment is not known. If palliative radiotherapy in short courses and for isolated fields is required to control symptoms not clearly related to disease progression, then study treatment administration should be withheld, if possible, for at least 1 week before radiation and for at least 1 week after its completion.

Participants should be closely monitored for any potential toxicity during and after receiving radiotherapy. Prior to resuming study treatment, radiotherapy-related AEs should resolve to Grade  $\leq$  1 or baseline, and participants must meet relevant eligibility criteria as determined by the BMS Medical Monitor (or designee) in discussion with the investigator. The BMS Medical Monitor (or designee) must be consulted prior to re-initiating study treatment in a participant with a dosing delay lasting  $>$  8 weeks from the previous dose.

Details of palliative radiotherapy should be documented in the source records and electronic case report form (eCRF). Details in the source records should include dates of treatment, anatomic site, dose administered and fractionation schedule, and AEs. Symptoms requiring palliative radiotherapy should be evaluated for objective evidence of disease progression. If a participant is considered to have progressed at the time of palliative therapy, then they must meet the treatment beyond progression criteria ([Section 5.1.4](#)) prior to re-initiating study treatment. Participants receiving palliative radiation of target lesions will have the evaluation of ORR just prior to radiotherapy, but these participants will no longer be evaluable for the determination of response subsequent to the date palliative radiation occurs.

For participants who need to undergo surgery during the study, it is recommended to hold study treatment(s) for at least 2 weeks before (if elective) and 2 weeks after surgery, or until the participant recovers from the procedure, whichever is longer. Participants undergoing major surgery for any reason while on study should have study treatment(s) held for at least 4 weeks after surgery. Prior to resuming study treatment wound healing must be evaluated by the surgeon, surgically related AEs should resolve to Grade 1 or baseline, and participants must meet relevant eligibility criteria as determined by the BMS Medical Monitor (or designee) in discussion with the investigator. The BMS Medical Monitor (or designee) must be consulted prior to re-initiating study treatment in a participant with a dosing delay lasting  $>$  8 weeks from the previous dose.

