## 2 RESPONSE CRITERIA

### 2.1 Evaluation of Target Lesions

- **Complete Response (CR):** Disappearance of all target lesions. Any pathological lymph nodes (whether target or non-target) must have reduction in short axis to < 10 mm.
- **Partial Response (PR):** At least a 30% decrease in the sum of diameters of target lesions, taking as reference the baseline sum diameters.
- **Progressive Disease (PD):** At least a 20% increase in the sum of diameters of target lesions, taking as reference the smallest sum on study (this includes the baseline sum if that is the smallest on study). In addition to the relative increase of 20%, the sum must also demonstrate an absolute increase of at least 5 mm. (Note: the appearance of one or more new lesions is also considered progression).
- **Stable Disease (SD):** Neither sufficient shrinkage to qualify for PR nor sufficient increase to qualify for PD, taking as reference the smallest sum diameters while on study.
- **Not Evaluable (NE):** If one or more target lesions cannot be measured or adequately assessed as either fully resolved or too small to measure (due to missing or poor quality images), and the sum of diameters of the remaining measured target lesions (if any) has not increased sufficiently to meet Progressive Disease as defined above.

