##### 2.1.1.2 *Target lesions that become 'too small to measure'*

While on study, all lesions (nodal and non-nodal) recorded at baseline should have their actual measurements recorded at each subsequent evaluation, even when very small (eg, 2 mm). However, sometimes lesions or lymph nodes which are recorded as target lesions at baseline become so faint on CT scan that the radiologist may not feel comfortable assigning an exact measure and may report them as being 'too small to measure'. When this occurs it is important that a value be recorded on the case report form. If it is the opinion of the radiologist that the lesion has likely disappeared, the measurement should be recorded as 0 mm. If the lesion is believed to be present and is faintly seen but too small to measure, a default value of 5 mm should be assigned as the reference diameter. (Note: It is less likely that this rule will be used for lymph nodes since they usually have a definable size when normal and are frequently surrounded by fat such as in the retroperitoneum; however, if a lymph node is believed to be present and is faintly seen but too

small to measure, a default value of 5 mm should be assigned in this circumstance as well). This default value is derived from the 5 mm CT slice thickness (but should not be changed with varying CT slice thickness). The measurement of these lesions is potentially non-reproducible, therefore providing this default value will prevent false responses or progressions based upon measurement error. To reiterate, however, if the radiologist is able to provide an actual measure, that should be recorded, even if it is below 5 mm.

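### Section 7.7.3 permits surgery as well as radiation to isolated lesions but stops response evaluation only after radiation, so a resected target lesion could count towards a false response in ORR

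*Combined protocol and SAP*

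**What the plan says.** Protocol Section 7.7.3 opens local control to two procedures: "Limited radiation treatment or surgery to control isolated lesions may be permitted for participants", after consultation with the Medical Monitor. It then gives one rule on response. "Participants receiving palliative radiation of target lesions will have the evaluation of ORR just prior to radiotherapy", and "these participants will no longer be evaluable for the determination of response subsequent to the date palliative radiation occurs". The surgery paragraph in the same section deals with treatment holds, wound healing, resolution of adverse events and the conditions for resuming study treatment. It does not mention response.

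Appendix 5 defines target-lesion CR as "Disappearance of all target lesions" and PR as "At least a 30% decrease in the sum of diameters of target lesions, taking as reference the baseline sum diameters". Neither definition asks why a lesion is no longer there. Its Section 2.1.1.2 adds: "If it is the opinion of the radiologist that the lesion has likely disappeared, the measurement should be recorded as 0 mm". NE for target lesions is tied to images that are missing or of poor quality. Resection is not mentioned.

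ORR is the Part 2C primary endpoint, by BICR (Table 4-1), and the basis of the sample size in Parts 2A and 2B (Sections 10.1.4 and 10.1.5). Table 10.3.1-1 takes it over all treated participants, counting those whose best overall response (BOR) is CR or PR.

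**The concern.** The radiation sentence shows that the sponsor already accepts the principle: once a target lesion has been treated locally, later shrinkage cannot be credited to the study drug. The rule was written for only one of the two local therapies that the same section allows. Surgery is the plainer case, because it takes the lesion out altogether and study treatment may resume afterwards.

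If a reader applies Appendix 5 as written to a clean post-operative scan, the sum of diameters falls by the size of the removed lesion. The participant can then meet the PR threshold, or CR, with no drug effect. The error would enter BOR and therefore ORR. Central blinded reading hides the treatment arm, but it does not supply a scoring rule that the criteria lack.

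**Working it through.** The plan states no figure on this point to reproduce. The Part 2C power statements (about 80%, or about 73% without borrowing) are not in dispute and cannot be re-derived, since the sample sizes and the ORR difference are redacted. The check is a comparison of the text, followed by arithmetic on the plan's own PR rule.

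**1. The two local therapies side by side (Section 7.7.3)**

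| | Radiation | Surgery |
|---|---|---|
| Permitted to isolated lesions | Yes | Yes |
| Study treatment may resume | Yes | Yes |
| Response taken from before the procedure | Yes, for target lesions | Not stated |
| Not evaluable for response afterwards | Yes | Not stated |
| Details required in the eCRF | Yes | Not stated |

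**2. Scoring a resected target lesion under Appendix 5**

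- *NE?* Section 2.1 links NE to missing or poor-quality images. A good post-operative scan is neither.
- *0 mm?* Section 2.1.1.2 gives this value to a lesion judged likely to have disappeared. The text concerns lesions that have become too faint to measure, so applying it to resection is an inference. It is, however, the nearest rule available.
- *Confirmation?* Sections 2.3.3 and 2.3.4 require the criteria to be met again at least 28 days later. A removed lesion stays absent, so this step does not filter the case out.
- *Overall response?* Under Table 2.3.2-1, new lesions or non-target progression give PD whatever happens to the target lesions. Target CR with persisting non-target disease gives PR. Overall CR needs non-target CR as well.

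**3. When resection alone meets the PR threshold**

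Hold the other target lesions at their baseline size and set the resected one to 0 mm.

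Percentage fall = 100 × (resected diameter) / (baseline sum), compared with 30%.

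For *k* equal target lesions with one resected, the fall is 100/*k*. Section 1.4 allows at most five target lesions, two per organ.

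| Equal target lesions | Fall | At least 30%? |
|---|---|---|
| 1 | 100% | Yes (target-lesion CR) |
| 2 | 50% | Yes |
| 3 | 33.3% | Yes |
| 4 | 25% | No |
| 5 | 20% | No |

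Unequal lesions, with assumed sizes:

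- 40 + 30 mm, the 30 mm lesion resected: 30/70 = 42.9%, meets the threshold.
- 50 + 20 + 20 mm, a 20 mm lesion resected: 20/90 = 22.2%, does not.
- 60 + 20 + 20 + 15 + 15 mm, the 60 mm lesion resected: 60/130 = 46.2%, meets it.
- The same five lesions, a 15 mm lesion resected: 15/130 = 11.5%, does not.

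So the threshold can be met at any number of target lesions, but only if the removed lesion is a large enough share of the baseline sum.

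**4. Effect on ORR**

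One false responder among *n* treated participants adds 100/*n* percentage points. Arm sizes are redacted, so *n* is assumed: 100/20 = 5.0, 100/40 = 2.5, 100/100 = 1.0.

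**The case against.** The strongest reply is that the gap is narrow and may be closed elsewhere.

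- **BOR ends at progression.** Appendix 5, Section 2.3.1 counts responses only up to progression, and Section 5.1.4.1 fixes Investigator-assessed progression at the first event. Palliative surgery often follows progression, and scans after that point cannot create a response. This stands: only surgery on a target lesion before progression matters.
- **Censoring for subsequent therapy.** Section 2.3.1 also makes BOR subject to such censoring. But the term is not defined there, and Section 5.1.3.3 and Table 2-3 use similar wording for treatments recorded in follow-up. Surgery under Section 7.7.3 is permitted during study treatment. If the general phrase were enough, the radiation sentence would not be needed.
- **Documents not seen.** The separate SAP announced in Section 10.3 or the Imaging Manual could hold a rule. That is possible. The censoring detail that Section 10.3.1 defers to the SAP names only time-to-event endpoints; the list is given as examples, so it does not settle the matter.
- **Few cases.** Surgery needs consultation with the Medical Monitor. This also stands, and no frequency can be derived from the documents.

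Three stronger readings are tempting. A reader might infer that the protocol instructs readers to enter 0 mm for a resected lesion. It does not; that value is written for lesions too small to measure. A reader might infer a bias between arms in Part 2C because it is open label. Different use of surgery by arm is conceivable, but nothing in the documents shows it. A reader might size the effect on a cohort of 40, the number in Section 10.3.8.1. That number belongs to the safety-monitoring boundary and is not a stated size for an ORR analysis.

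**Conclusion.** The concern holds as a scope gap in a rule that the plan already has. Section 7.7.3 permits both procedures and protects response evaluation after only one. Appendix 5 followed literally could turn a resection into a confirmed PR or, if all target and non-target disease is gone, a CR.

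This requires surgery on a target lesion before progression, no new lesions and no non-target progression. It also requires a removed lesion of at least 30% of the baseline sum, if the other target lesions are unchanged. The effect per case is 5.0 to 1.0 percentage points of ORR for assumed arms of 20 to 100. The total effect cannot be estimated, because neither the frequency of such surgery nor the arm sizes are given; it is probably small. The point is still worth correcting, because the endpoint is primary in Part 2C and the repair follows the sponsor's own reasoning for radiation.

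**What to change.** - **Section 7.7.3:** extend the radiation sentence to surgery or any other local therapy of a target lesion. BOR is taken from assessments before the procedure, and later assessments cannot establish a response. State that the participant stays in the ORR denominator, in keeping with the all-treated definition in Table 10.3.1-1.
- **Appendix 5:** state that a target lesion resected or otherwise locally treated is NE from then on, not 0 mm. Its NE definition already leaves room to call progression on the remaining lesions, so progression can still be assessed.
- **Both reads:** apply the same rule to Investigator and BICR assessments, and carry it into the Imaging Manual and the SAP.
- **eCRF:** record the date and lesion site of on-study surgery. A reader might assume that this is already collected, but Section 7.7.3 asks for such details only for palliative radiotherapy. The rule cannot be applied reliably without them.

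The cost is a few sentences and a small eCRF addition. No scan or visit is added, and no change is proposed to when surgery is allowed or how treatment is managed around it.
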